## 8.2 Statistical analysis of the secondary efficacy variables

### 8.2.1 Derivations of secondary efficacy variables

#### 8.2.1.1 PASI75 Responder at Week 4

A categorical response variable, PASI75 at Week 4 is defined to be equal to 1 if the percentage improvement from Baseline to Week 4 in the PASI scores is 75% or greater and 0 if the percentage improvement from Baseline to Week 4 is less than 75%. The definition of percentage improvement from Baseline is given in Section 8.1.1.1.

#### 8.2.1.2 PASI90 Responder at Week 16

A categorical response variable, PASI90 at Week 16 is defined to be equal to 1 if the percentage improvement from Baseline to Week 16 in the PASI scores is 90% or greater and 0 if the percentage improvement from Baseline to Week 16 is less than 90%.

The definition of percentage improvement from Baseline is given in Section 8.1.1.1.

#### 8.2.1.3 PASI100 Responder at Week 48

PASI100 response definition and derivation are outlined in Section 8.1.1.1 and Section 8.1.1.2.

#### 8.2.1.4 IGA Response (0/1) at Week 16

A static IGA for psoriasis will be used to assess disease severity in all subjects during the study. The Investigator will assess the overall severity of psoriasis using the following five-point scale:

**Table 8–1: Investigator’s Global Assessment**

Score	Short Descriptor	Definition
0	Clear	No signs of psoriasis; post-inflammatory hyperpigmentation may be present
1	Almost clear	No thickening; normal to pink coloration; no to minimal focal scaling
2	Mild	Just detectable to mild thickening; pink to light red coloration; predominately fine scaling
3	Moderate	Clearly distinguishable to moderate thickening; dull to bright red, clearly distinguishable to moderate thickening; moderate scaling
4	Severe	Severe thickening with hard edges; bright to deep dark red coloration; severe/coarse scaling covering almost all or all lesions

IGA response at Week 16 is defined as clear [0] or almost clear [1] with at least a two-category improvement from Baseline at Week 16.

### 8.2.2 Primary analysis of the secondary efficacy variables

All secondary efficacy variables are binary (responder) variables and will be summarized using frequency tables by randomized treatment group for each visit. Primary analysis for secondary efficacy variables will be summarized based on imputed data (NRI for binary variables) and for the RS, unless otherwise specified. A stratified CMH test will be performed, where region and prior biologic exposure (yes/no) will be used as stratification variables.

Treatment comparisons between bimekizumab and secukinumab will be made based on the CMH test using the p-value for the general association. PASI90 and IGA (clear or almost clear) at Week 16 are not in the closed testing procedure therefore the related p-values should only be considered descriptive statistics.

PASI100 at Week 48 is the only secondary variable that is affected by the re-randomization at Week 16. The way the analysis for this variable is conducted will depend on which comparison is being made. The following comparisons will be performed:

- Compare all subjects initially randomized to bimekizumab (regardless of re-randomization assignment at Week 16) to all subjects initially randomized to secukinumab based on the RS (H4)
- Compare subjects who were assigned to bimekizumab 320mg Q4W at Week 16 to subjects on secukinumab based on the MS (H5)
- Compare subjects who were assigned to bimekizumab 320mg Q8W at Week 16 to subjects on secukinumab based on the MS (H6)

### **8.2.3 Sensitivity analyses of the secondary efficacy variables**

For all secondary efficacy variables, sensitivity analyses #1 and #2 (Section 8.1.3.1 and Section 8.1.3.2) will be performed. In addition, for PASI100 response at Week 48, the sensitivity analyses described in Section 4.2.1.7 will be performed.

### **8.3 Analysis of other efficacy variables**

The other efficacy variables are listed below and will be evaluated according to the planned assessments in the protocol. This excludes the time points for the primary and secondary variables specified above in Section 8.1.1.2 and Section 8.2.1.

Three different types of tables will be produced by visit through Week 48:

1. Subjects in the MS summarized by the 3 maintenance treatment groups (bimekizumab 320mg Q4W, bimekizumab 320mg Q8W, and secukinumab).
2. A subset of Group 1 above. Specifically, this will include only those subjects who are responders at Week 16 for the variable being summarized.
3. Subjects in the RS summarized by the 2 randomized treatment groups (bimekizumab and secukinumab).

All efficacy variables will be summarized in the manner described for Group 1 and Group 3 above. Summaries for Group 2 will be done only for a subset of efficacy variables, namely, PASI90/100 responder rate, IGA Clear or Almost Clear. Examination of subgroups will only be done for Group 3.

Binary (responder) variables will be summarized using frequency tables by treatment group for each visit. Continuous variables will be summarized using descriptive statistics by treatment group for each visit. All variables will be summarized based on imputed data (NRI and MCMC/Monotone Regression for binary and continuous variables, respectively), unless otherwise specified.

For variables that are part of the sequence testing procedure, summaries based on observed case data will also be provided. There may be cases where the multiple imputation model fails to converge. In such situations, the LOCF approach will instead be used to impute the missing data. Selected efficacy variables will also be summarized by visit through Week 144 for the OLE Period for the OLS. Subjects will be summarized by treatment sequence comprising randomized treatment at Baseline and OLE period treatment at Week 48.

The OC approach will be used to summarize the following efficacy variables for subjects in the OLE2 treatment period: PASI90, PASI100, IGA (0/1), IGA (0), DLQI (0/1), and PSD response.

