### 4.2 Handling of dropouts or missing data

#### 4.2.1 Handling of missing data for efficacy variables

Based on previous studies of biologics in subjects with moderate to severe chronic plaque psoriasis, it is expected that the number of subjects who discontinue prior to Week 16 will be low. For the small percentage of subjects for whom primary endpoint data are unavailable at Week 16, this lack of data is suggestive of an ineffective study treatment, thereby supporting the imputation of nonresponse. Achieving the clinical response and making it through 16 weeks of study treatment are both critical components of the primary outcome. Therefore, non-responder imputation (NRI) is considered an appropriate method for handling missing data.

If a subject discontinues early from the study, all efficacy data that are collected later than 35 days after the last administration of study treatment will be treated as missing and subject to imputation as applicable.

Study variables with multiple components may have rules to account for partial missing data of 1 or more components. Such rules will be defined in section 8 for applicable endpoints. The following rules are outlined for cases where variables are completely missing, including partial missing data where the data handling rules conclude that the variable should be treated as completely missing.

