#### **4.2.1.3 Handling missing data for the other efficacy variables**

For other binary efficacy variables, missing data will be imputed using NRI as primary method.

For other continuous efficacy variables, multiple imputation (MI) will be used to impute missing data when possible. If the imputation model cannot converge, last observation carried forward (LOCF) will be used. The MI procedure will be similar to sensitivity analysis #1 described in Section 8.1.3.1 with the following differences:

1. No dichotomization will be necessary.
2. Instead of using the stratified Cochran-Mantel-Haenszel (CMH) test, the imputed data sets will be combined, and simple means and standard errors will be calculated using Rubin's rules (via SAS PROC MIANALYZE). For calculation of other descriptive statistics such as the median, minimum and maximum, Rubin's rules do not apply. Multiple imputation estimates will be computed by simply averaging the estimates from the multiple repetitions of the imputation algorithm.

For other ordinal variables (IGA score, EQ-5D-3L and Patient Global Assessment of PSO), OC method will be applied as the primary analysis method. No imputation is applied.

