#### 4.2.1.5 Missing data overview and summary

In summary, the approaches listed below will be used in this study for handling missing data for efficacy variables as appropriate:

- NRI: Subjects who have missing data at the time point of interest are treated as though they did not respond to the treatment.
- MI –MCMC / Monotone Regression: Using multiple imputation methodology, intermittent missing data are imputed based on the MCMC method, and monotone missing data are imputed using monotone regression. Note: for all analyses and summaries using MI, subjects with missing baseline value will be excluded.
- LOCF: Post-Baseline missing data are imputed by carrying forward the last available observation (including Baseline).
- OC: Missing data are not imputed. Only subjects with available data who have not discontinued study treatment at the given time point are considered.

The following table depicts which missing data handling approaches should be used based on variable priority (primary, secondary, other) and variable type (responder, continuous, ordinal).

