**Table 4–1: Missing data handling approach by variable priority and type**

Variable Priority	Variable Type	NRI	MI (MCMC/ Monotone Regression)	LOCF	OC
Primary	Responder	P	S a	S	S
Secondary	Responder	P	S a	B	S
Other	Responder	P			S b,c
	Continuous e		P	B	
	Ordinal				P d

P=Primary method, S=Sensitivity method, B=Backup method, NRI=Nonresponder imputation, MI=Multiple imputation, MCMC=Markov Chain Monte Carlo, LOCF=Last observation carried forward, OC=Observed Case  
Note: Backup method is only applicable when the primary/secondary method is unable to converge due to challenges with the imputation model.

Note: Additional missing data handling approaches are detailed in Section 4.2.1.7 for assessing the impact of COVID-19 on the secondary efficacy variable PASI100 response at Week 48.

a Imputation method is applied on continuous data, and responder variable is derived from the continuous variable based on complete data set.

b Only applies to by-visit summaries of variables that are in the multiplicity-controlled testing procedure.

c Includes IGA Responses, PASI75, PASI90 and PASI100.

d Includes IGA score, Patient Global Assessment of PSO and EQ-5D-3L.

e For PASE, OC is the primary analysis method.

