**Randomized Set:** When programming multiple imputations based on the RS, PROC MI will be used with a separate data set for each of the 2 randomized treatment groups (bimekizumab 320mg Q4W and secukinumab) including all scheduled assessment visits from Baseline to Week 48.

**Maintenance Set:** When programming multiple imputation based on the MS, PROC MI will be used with a separate data set for each of the 3 Maintenance Period treatment groups

(bimekizumab 320mg Q8W, bimekizumab 320mg Q4W, secukinumab) including all scheduled assessment visits from Baseline to Week 48.

Open-Label Set: When programming multiple imputations based on the OLS, PROC MI will be used with a separate data set for each of the 6 treatment sequences based on the combination of randomized treatment at Baseline, Maintenance Period treatment and OLE period treatment at Week 48 including all scheduled assessment visits from Baseline to Week 144. However, the summary values for the 4 treatment sequences based on the combination of randomized treatment at Baseline and OLE period treatment at Week 48 will be computed after the imputation steps

The Open-label Set 2: The analyses will be based on OC. Multiple imputation methods described above will not be applied.

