#### **4.8 Examination of subgroups**

Subgroup analyses will be based on data up to Week 48 only. These analyses will be performed on the PASI75/90/100 response rates, using by visit summaries only. The following subgroups for analysis will be determined for the RS using baseline data:

- Age (<40 years, 40 to <65 years, ≥65 years)
- Gender (male, female)
- Disease duration (<median, ≥median)
- Region (North America, Western Europe, Central/Eastern Europe, Asia/Australia)
- Weight (≤100 kg, >100 kg)
- Body mass index (BMI) (<25 kg/m^2, 25 to <30 kg/m^2, ≥30 kg/m^2)
- Prior systemic phototherapy or chemotherapy (yes, no)
- Prior biologic exposure (yes, no)
- Prior primary failure to biologic (yes/no)
- Prior systemic therapy of any kind (yes, no)
- Baseline disease severity (PASI<20, PASI≥20)
- Antibody positivity (negative, positive)

Antibody positivity is the only subgroup that is not determined by Baseline data (described in Section 9.3.2). It will be presented in a separate table.

The definition of prior systemic therapy of any kind is if a subject received previous biologic therapy, previous systemic therapy (non-biologic), or previous systemic chemotherapy or phototherapy. Subjects who never received previous biologic therapy, previous systemic therapy (non-biologic), or previous systemic chemotherapy or phototherapy will be classified as not receiving prior systemic treatment for psoriasis.

In addition, in order to assess whether an early response to treatment is predictive of response at later time points, subgroup analyses will be performed for PASI90/100 and IGA over time using the following early response subgroups:

- PASI75 response (OC) at Week 4 (yes, no) to predict PASI90/100 and IGA (clear or almost clear) (NRI) through Week 48 based on RS
- PASI90 response (OC) at Week 16 (yes, no) to predict PASI100 (NRI) through Week 48 based on RS
- PASI90 response (OC) at Week 48 (yes, no) to predict PASI90 (NRI) during the OLE based on OLS
- PASI90 response (OC) at Week 48 (yes, no) to predict PASI100 (NRI) during the OLE based on OLS
- PASI90 response (OC) at Week 48 (yes, no) to predict IGA responder rates (clear) and IGA responder (clear or almost clear) during the OLE based on OLS.

All summaries will be based on imputed data as appropriate and will include descriptive statistics only.

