### 8.3.1.3 PASI score

Absolute and percent change from Baseline in PASI score is defined in Section 8.1.1.1.

The percentage of subjects with absolute PASI score  $\leq 1$ ,  $\leq 2$ ,  $\leq 3$  and  $\leq 5$  will be presented over time using NRI for the RS, the MS, and the OLS.

Absolute PASI score categories will not be summarized for the OLE2 treatment period.

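### OLE2 response rates are summarised by observed cases only, with no fixed-denominator (NRI) summary beside them, and the PSD rule in SAP 8.3.8 conflicts with this

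*SAP*

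**What the plan says.** SAP 8.3 fixes the OLE2 method for six response variables (PASI90, PASI100, IGA 0/1, IGA 0, DLQI 0/1 and PSD response): "The OC approach will be used to summarize the following efficacy variables for subjects in the OLE2 treatment period". The OLS2 paragraph at the end of SAP 4.2.1.6 says the same: "The analyses will be based on OC. Multiple imputation methods described above will not be applied". SAP 4.2.1.5 defines OC: "Only subjects with available data who have not discontinued study treatment at the given time point are considered".

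The general rule differs. SAP 4.2.1.3 says: "For other binary efficacy variables, missing data will be imputed using NRI as primary method". Table 4-1 marks NRI as primary for other responder variables. It allows OC only as a sensitivity method, with the footnote "Only applies to by-visit summaries of variables that are in the multiplicity-controlled testing procedure" and a further footnote naming the IGA and PASI responses. DLQI 0/1 and PSD response are not named there, and the table has no OLE2 exception.

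NRI is applied in the OLE itself. SAP 4.8 has "PASI90 response (OC) at Week 48 (yes, no) to predict PASI90 (NRI) during the OLE based on OLS", and SAP 8.3.1.3 has the absolute PASI categories, which "will be presented over time using NRI for the RS, the MS, and the OLS".

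For PSD response, SAP 8.3.8 has missing scores imputed by NRI without naming a period, and the same section provides for PSD response summaries in OLE2.

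**The concern.** Under OC a subject who stops treatment leaves both numerator and denominator. If subjects tend to stop because they are not responding, the remaining denominator is partly selected on outcome. SAP 4.2.1.6 notes that investigators may take non-responders off treatment, so this is plausible. The OLE2 percentage then describes response among those still treated, not among those who entered OLE2, and no planned table gives the second quantity.

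The final report brings the OLE and OLE2 together, so a reader will see NRI-based rates for one and OC-only rates for the other. The matter is most sensitive for the Group B subjects who restart treatment with IGA of 3 or more, because those who do not regain response could be among those who leave. For PSD response there is also a programming problem: 8.3 and 8.3.8 cannot both be followed in OLE2.

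**Working it through.** The SAP states no dropout or response rate for OLE2, so there is no figure of its own to reproduce. The inputs below are assumptions, shown over a range.

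**Definitions.** At a given visit, N is the number of subjects in an OLS2 column, d the share of them not counted under OC, and r the number of observed responders.

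- OC = r / (N(1 − d))
- NRI = r / N = OC × (1 − d)
- Gap = OC − NRI = d × OC

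The numerator is the same and the OC denominator is smaller or equal, so OC is never below NRI on the same data. This requires both summaries to treat a mapped early-withdrawal visit in the same way.

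**Gap in points (d × OC), assumed inputs:**

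| Dropout d | OC 60% | OC 75% | OC 90% |
|---|---|---|---|
| 5% | 3.0 | 3.75 | 4.5 |
| 10% | 6.0 | 7.5 | 9.0 |
| 15% | 9.0 | 11.25 | 13.5 |
| 20% | 12.0 | 15.0 | 18.0 |

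The same relation from the other side: 70 responders among 100 treated is 70% under NRI. Under OC it is 70/95 = 73.7%, 70/90 = 77.8%, 70/85 = 82.4% or 70/80 = 87.5% at 5%, 10%, 15% or 20% dropout.

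**Bias against the rate in all treated subjects.** Let q be the share of leavers who would be responders at that visit. The target rate is (1 − d) × OC + d × q, so:

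- bias of OC = d × (OC − q)
- bias of NRI = −d × q

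With d = 10% and OC = 75% (NRI = 67.5%):

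| q | Target rate | Bias of OC | Bias of NRI |
|---|---|---|---|
| 0% | 67.5% | +7.5 | 0 |
| 25% | 70.0% | +5.0 | −2.5 |
| 50% | 72.5% | +2.5 | −5.0 |
| 75% | 75.0% | 0 | −7.5 |

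As long as leavers respond no better than stayers, the two summaries bracket the target. Neither alone does.

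**The early-withdrawal visit.** SAP 3.3 assigns an early-withdrawal visit to the next scheduled visit and counts it as observed there, which sits awkwardly with the OC definition in 4.2.1.5. It keeps a leaver in the denominator for one visit at most. Under the rule in 4.2.1 that efficacy data more than 35 days after the last dose become missing, a withdrawal visit one full 8-week interval (56 days) after the last dose would not count at all.

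**The case against.** The strongest reply is that OC in OLE2 is a deliberate choice. SAP 8.3 sets NRI for binary variables subject to exceptions, then names one, and 4.2.1.6 repeats it. A specific rule overrides a general one. This stands for five of the six variables. For PSD response the specific section itself says NRI, so the conflict remains.

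Second, NRI is not the truth either: it is too low by d × q. SAP 4.2.1.6 also argues that in many cases missingness should depend only on observed scores. The statement in 4.2.1 that "this lack of data is suggestive of an ineffective study treatment, thereby supporting the imputation of nonresponse" was written for the Week 16 primary endpoint, not for an extension after Week 144. All of this stands. It is a reason to show both summaries and not to rank one as correct.

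Third, OLE2 has no comparator and no hypothesis test. Denominators are displayed (SAP 3.1), and discontinuation reasons are summarised for OLS2 (SAP 5.1), so attrition is visible and an NRI-type rate can be approximated by hand for PASI and IGA. This stands and limits the weight of the point.

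Three stronger readings are tempting, and the document does not support them:

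- **That the OLE2 rate can only rise over time.** A treated subject who loses response stays in the OC denominator as a non-responder, so the rate can fall.
- **That the change of method produces an artificial step at Week 144.** OLE and OLE2 outputs are produced separately, on different sets and columns. OLS2 holds only US and Canadian subjects who reached Week 144, so the series would not be continuous under NRI either. OC summaries may also exist in the OLE for the PASI and IGA responses.
- **That the gap can be judged against the primary treatment effect.** A between-arm difference at Week 16 is no yardstick for a single-group percentage.

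**Conclusion.** The point holds as a reporting gap and a wording conflict, not as an error that touches any confirmatory result. OLE2 response is reported only among subjects still on treatment with data, and no fixed-denominator summary is planned. By arithmetic OC exceeds NRI by d × OC, which is 3 to 18 points over assumed dropout of 5% to 20% and OC rates of 60% to 90%. Whether OC overstates the rate in all treated subjects depends on q. At 10% dropout and OC of 75% the overstatement runs from 0, if leavers respond like stayers, to 7.5 points, if none would respond. An upward bias is plausible but not established, and its size cannot be fixed without OLE2 dropout figures.

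Replacing OC as the main OLE2 method is a debatable trade-off and does not follow from this. Adding NRI beside it is a clear improvement.

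**What to change.** - **Add an NRI summary on OLS2** for the six response variables beside the retained OC summary. The denominator is fixed: all OLS2 subjects in the column and, for DLQI and PSD, those who meet the eligibility rules used in the OLE. No multiple imputation is needed.
- **Reconcile the text.** State the OLE2 exception in SAP 4.2.1.3 and Table 4-1, and align the NRI rule for PSD response in 8.3.8 with 8.3 and the OLS2 paragraph of 4.2.1.6.
- **Say in one sentence** whether a mapped early-withdrawal visit (3.3) counts under OC (4.2.1.5), and apply the same rule to both summaries.

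The cost is SAP wording and one extra set of OLE2 tables, using NRI logic already needed for the OLE. The downside is that visits missed for administrative reasons count as non-response in the NRI table. The OC table beside it shows how much that matters.

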### **8.3.1 PASI**

#### **8.3.1.1 PASI75, PASI90 and PASI100 response rates**

Categorical response variables, PASI75, PASI90 and PASI100 over time are defined to be equal to 1 if the percentage improvement from Baseline to visit time point in the PASI scores is 75%, 90% and 100% respectively or greater and 0 if the percentage improvement from Baseline to visit time point is less than 75%, 90% and 100% respectively (1 = responder, 0 = non-responder).

The definition of PASI score percentage improvement from Baseline is given in Section 8.1.1.1.

A line plot of the PASI responder (PASI75, PASI90, and PASI100) rate over time, by treatment group will be produced for the RS and by randomized treatment groups. Additional plots will be produced separately for the MS by maintenance treatment groups, for the OLS and for the OLS2 (excluding PASI75) by OLE and OLE2 treatment sequence respectively.

